4.3. Sample Size and Power

In Part 2, approximately 600 infant participants 12 weeks to < 6 months of age will be enrolled at the dose level selected for Part 2, with an mRNA-1273.214 to placebo ratio of 1:1. Assuming 10% to 15% participants are not negative SARS-CoV-2 status at baseline, it is estimated that there will be a minimum of approximately 250 evaluable participants in the mRNA-1273.214 arm eligible for immunogenicity analyses.

The sample size of approximately 300 infant participants in the mRNA-1273.214 arm in Part 2 is considered to be sufficient to support a safety assessment. There is at least 90% probability to observe at least 1 participant with an AE at a true AE rate of 1% in this group.

The sample size calculation for each of the 2 primary noninferiority hypothesis tests (H_A^1 and H_A^2) was performed, and the larger sample size was chosen for the study.

• With approximately 250 evaluable participants receiving mRNA-1273.214 in the Per-Protocol Immunogenicity Subset - Negative (PPIS-Neg) in Study mRNA-1273-P206 and adults (≥ 18 years of age) in Study mRNA-1273-P301, there will be at least 90% power to demonstrate noninferiority of the immune response against Omicron variant, as measured by the geometric mean concentration (GMC) or GM level, in infant population at a 2-sided alpha of 0.05, compared with that in adults (≥ 18 years of age) in Study mRNA-1273-P301 receiving mRNA-1273, assuming an underlying geometric mean ratio (GMR) (which is calculated as ratio of GMC or

- GM level) value of 1 and the standard deviation of the natural log-transformed concentration/level is assumed to be 1.0, and a noninferiority margin of > 0.667.
- With approximately 250 evaluable participants receiving mRNA-1273.214 in the PPIS-Neg in Study mRNA-1273-P206 and adults (≥ 18 years of age) in Study mRNA-1273-P301, there will be at least 90% power to demonstrate noninferiority of the immune response against Omicron variant as measured by SRR in infants at a 2-sided alpha of 0.05, compared with SRR against Omicron variant in adults ≥ 18 years of age in Study mRNA-1273-P301 receiving mRNA-1273, assuming SRR of 60% to 70% in Study mRNA-1273-P301, true SRR improvement of 10% in infants from Study mRNA-1273-P206 compared with adults from Study mRNA-1273-P301, and a noninferiority margin of 5%.

4.4. Randomization

Random assignment of participants in Part 2 of the study will use a centralized interactive response technology (IRT), in accordance with pre-generated randomization schedules. Approximately 600 participants will be randomized in a 1:1 ratio to the mRNA-1273.214 arm or placebo arm (n = approximately 300 participants in each group).

4.5. Blinding and Unblinding

This study is conducted in two parts. Part 1 of this study will be open-label and blinding procedures will not be applicable.

Part 2 of this study will be conducted in an observer-blind manner. The investigator, study staff, study participants, study site monitors, and Sponsor personnel (or its designees) will be blinded to the IP administered until study end, with certain exceptions (please refer to Section 9.1 of the protocol for details).

At the time of interim analysis, only pre-identified Sponsor and unblinded Contract Research Organization (CRO) team members as specified in the study Data Blinding Plan will be unblinded to review treatment level results and individual listings. Please also refer to Section 6.6. Study sites will remain blinded to individual treatment assignments until the end of the study.

If a COVID-19 vaccine (mRNA-1273 or other) is authorized or licensed for infants, parent(s)/legally authorized representative(s) (LAR) of eligible study participants (by virtue of their age) will be offered the opportunity to unblind via a phone call and learn what treatment the participant received, ideally after they have reached at least Day 85 in the

study. Participants who have received mRNA-1273.214 will continue in the study and will be followed per protocol. If a participant previously received placebo, then their parent(s)/LAR(s) will be advised to discuss with the participant's primary care physician and follow current Centers for Disease Control and Prevention (CDC) recommendations regarding COVID-19 immunization. If a participant who received placebo in the study chooses to receive a non-study COVID-19 vaccine, they will be withdrawn from the study.

5. Analysis Populations

The following analysis sets are defined for Part 1 open-label phase and Part 2 blinded phase:

- Randomization Set
- Full Analysis Set (FAS)
- Modified Intent-to-Treat (mITT) Set
- Modified Intent-to-Treat-1 (mITT-1) Set
- Per-Protocol (PP) Set
- Immunogenicity Set
- Per-Protocol Immunogenicity Subset (PPIS)
- PPIS-Neg Set
- Safety Set
- Solicited Safety Set

5.1. Randomization Set

The Randomization Set consists of all participants who are randomized in Part 2 of the study, regardless of the participant's treatment status in the study. Participants will be analyzed according to the treatment group to which they were randomized.

5.2. Full Analysis Set

The Full Analysis Set (FAS) for Part 1 consists of all enrolled participants who receive at least 1 injection of IP, and the FAS for Part 2 consists of all randomized participants who receive at least 1 injection of IP. Participants will be analyzed according to the treatment group for the treatment they actually received in Part 1 and will be analyzed according to the treatment group to which they were randomized in Part 2.

5.3. Modified Intent-to-Treat (mITT) Set

The Modified Intent-to-Treat (mITT) Set consists of all participants in the FAS who had no serologic or virologic evidence of prior SARS-CoV-2 infection (both negative RT-PCR test for SARS-CoV-2 and negative serology test based on bAb specific to SARS-CoV-2 nucleocapsid) at baseline, i.e., all FAS participants excluding those with positive or missing RT-PCR test or serology test at baseline.

Participants in Part 2 will be analyzed according to the treatment group to which they were randomized.

5.4. Modified Intent-to-Treat-1 (mITT-1) Set

The Modified Intent-to-Treat-1 (mITT-1) Set consists of all participants in the mITT Set excluding those who received wrong treatment (i.e., at least one dose received that is not as randomized or planned).

Participants in Part 2 will be analyzed according to the treatment group to which they were randomized.

5.5. Per-Protocol (PP) Set

The Per-protocol (PP) Set consists of all participants in the FAS who meet all the following criteria:

- a) Received planned doses of IP per schedule
- b) Had no major protocol deviations that impact key or critical data
- c) Had a negative RT-PCR test for SARS-CoV-2 and negative serology test based on bAb specific to SARS-CoV-2 nucleocapsid protein at baseline

The PP Set will be used as the primary analysis population in the efficacy analyses unless otherwise specified. Participants will be analyzed according to the treatment group to which they were randomized in Part 2.

5.6. Immunogenicity Set

Immunogenicity Set (IS) consists of all participants in the FAS who provide immunogenicity samples.

5.7. Per-Protocol Immunogenicity Subset (PPIS)

PPIS consists of all participants in Immunogenicity Subset who meet all the following criteria:

- a) Received planned doses of IP per schedule
- b) Complied with the immunogenicity testing schedule
- c) Had baseline (Day 1) and Day 85 Ab assessments for the analysis endpoint
- d) Had no major protocol deviations that impact key or critical data

The PPIS will be used for sensitivity analyses or supportive analysis of immunogenicity data. Participants will be analyzed according to the treatment group which they actually received in Part 1 and to which they were randomized in Part 2.

5.8. Per-Protocol Immunogenicity Subset - Negative

Per-Protocol Immunogenicity Set - Negative (PPIS-Neg) includes participants in the PPIS who are SARS-CoV-2 negative (no serologic or virologic evidence of prior SARS-CoV-2 infection) before receiving the first dose of IP.

PPIS-Neg will serve as the primary population for the analysis of immunogenicity data.

5.9. Safety Set

The Safety Set consists of all enrolled (Part 1) or randomized (Part 2) participants who received at least one dose of IP. The Safety Set will be used for analysis of safety except for the solicited ARs. In addition, the following Safety Set is defined for each injection separately. The First Injection Safety Set consists of all subjects in the Safety Set who have received the first study injection. The Second Injection Safety Set consists of all subjects in the Safety Set who have received the second study injection. Participants will be included in the vaccination group corresponding to the vaccination they actually received. For a participant who was randomized to placebo in Part 2 but received any dose of mRNA-1273.214 at any injection, the participant will be included in the mRNA-1273.214 group in the Safety Set.

5.10. Solicited Safety Set

The Solicited Safety Set consists of all participants in the safety set who contribute any solicited AR data, i.e., have at least one postbaseline solicited safety assessment. The Solicited Safety Set will be used for the analyses of solicited ARs and participants will be

included in the vaccination group corresponding to the study injection they actually received. In addition, the following Solicited Safety Set is defined for each injection separately.

The First Injection Solicited Safety Set consists of all subjects in the Solicited Safety Set who have received the first study injection and have contributed any solicited AR data from the time of first study injection through the following 6 days.

The Second Injection Solicited Safety Set consists of all subjects in the Solicited Safety Set who have received the second study injection and have contributed any solicited AR data from the time of second study injection through the following 6 days. Participants will be analyzed according to the vaccination group a participant received, rather than the vaccination group to which the subject was randomized. A participant who was randomized to placebo but received any dose of mRNA-1273.214 at any injection will be included in the mRNA-1273.214 group in the Solicited Safety Set.

6. Statistical Analysis

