Emerging evidence suggests that although maternal antibodies are transferred to infants transplacentally after maternal vaccination, titers wane over the course of the first 6 months of life and are undetectable in up to 43% of infants at 6 months of age, supporting the need for early vaccination in this age group (Shook et al 2022). While observational data (Halasa et al 2022) demonstrate that maternal vaccination during pregnancy can be 61% effective (95% CI = 31%-78%) in preventing hospitalization of infants aged < 6 months, there are no systematic studies of the need and risk-benefit of infant immunization against COVID-19. Additionally, it remains unknown if transferred passive immunity after maternal immunization with vaccines targeting prototype SARS-CoV-2 confer benefit of protection against emerging variants to the infants. Hence, there remains a need for active immunization strategies in this age group.

In the ongoing Study mRNA-1273-P204 (data snapshot on 21 Feb 2022), the safety profile of the 2 dose primary series in children and toddlers/infants (6 months to < 6 years of age) was generally consistent with the known safety profile observed in other studies of mRNA-1273. In addition, the events commonly seen in this pediatric population consisted primarily of grade 1 and grade 2 reactogenicity occurring within 2 days after either dose lasting 2 to 3 days. Solicited local and systemic ARs in children 6 months to < 6 years of age were generally consistent with the AE profile of mRNA-1273 in older age groups with the exception of fever. Fever was most commonly reported on Day 1 or Day 2 after any vaccination and lasted for a median duration of 1 day. Beyond Day 2 (after any dose) fever rates were similar between the mRNA-1273 group and the placebo group. Although no studies to date have evaluated mRNA-1273.214 in young children, ongoing trials in adults have not raised any safety concerns. Based on experience to date, the risk-benefit profile of evaluating mRNA-1273.214 in younger children is favorable.

Protocol: mRNA-1273-P206, Original

The objective for this Phase 2 study is to evaluate the safety, tolerability, reactogenicity, and effectiveness of 2 dose levels (5 and 10 μ g) of mRNA-1273.214 vaccine or another modified vaccine (both referred to as 1273.214 in the document) administered as 2 doses 8 weeks apart in participants aged 12 weeks to < 6 months.

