8.10.2. Use of Electronic Diaries

At the time of consent, participants' parent(s)/LAR(s) must confirm they will be willing to complete an eDiary using either an application downloaded to their smartphone or using a device that is provided at the time of enrollment. Before enrollment on Day 1, participants' parent(s)/LAR(s) will be instructed to download the eDiary application or will be provided an eDiary device to record solicited ARs (Section 8.11.3) on Day 1. Based on availability, smartphone devices may be provided to those participants' parent(s)/LAR(s) who do not have their own device to use for eDiary activities.

At each injection visit, participants' parent(s)/LAR(s) will be instructed (Day 1) or reminded (Day 57) on thermometer (axillary and rectal) usage to measure body temperature, ruler usage to measure injection site erythema and swelling/induration (hardness), and assessment for localized axillary swelling or tenderness on the same side as the injection arm/thigh.

At each injection visit, participants' parent(s)/LAR(s) will record data into the eDiary starting approximately 30 minutes after injection under the supervision of the study site staff to ensure successful entry of assessments. The study site staff will perform any retraining as necessary. Participants' parent(s)/LAR(s) will continue to record data in the eDiary after they leave the study site, preferably in the evening and at the same time each day, on the day of injection and for 6 days following injection.

Participants' parent(s)/LAR(s) will record the following data in the eDiary:

Solicited local and systemic reactogenicity ARs, as defined in Section 8.11.3, that occur
on the day of each vaccine administration and during the 7 days after vaccine
administration (ie, the day of injection and 6 subsequent days). Capturing details of ARs
in the eDiary should not exceed 7 days after each vaccination. If a solicited local or

Protocol: mRNA-1273-P206, Original

systemic AR continues beyond Day 7 after vaccination, the event should be reviewed by the study site staff either via a telemedicine visit/call or at an unscheduled study site visit.

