6.1. General Considerations

The Schedule of Assessments is provided in Appendix E for Part 1 and 2.

Continuous variables will be summarized using the following descriptive summary statistics: the number of subjects (n), mean, standard deviation (SD), median, minimum (min), and maximum (max). For the summary statistics of all numerical variables unless otherwise specified, the display precision will follow programming standards. Please see Appendix A for variable display standards.

Categorical variables will be summarized using counts and percentages. When count data are presented, the percentage will be suppressed when the count is zero in order to draw attention to the non-zero counts. A row denoted "Missing" will be included in count tabulations where specified on the shells to account for dropouts and missing values. The denominator for all percentages will be the number of subjects in that vaccination group within the analysis set of interest, unless otherwise specified.

Baseline value, unless specified otherwise, is defined as the most recent non-missing measurement (scheduled or unscheduled) collected before the first dose of IP. For immunogenicity tests and nasal swab tests, the baseline is defined as the most recent non-missing measurement (scheduled or unscheduled) collected before or on the date of first dose of IP (Day 1) prior to the first dose of IP.

Baseline SARS-CoV-2 status is determined by using virologic and serologic evidence of SARS-CoV-2 infection on or before Day 1.

Positive SARS-CoV-2 status at Baseline is defined as a positive RT-PCR test for SARS-CoV-2, and/or a positive serology test based on bAb specific to SARS-CoV-2 nucleocapsid on or before Day 1.

Negative status at Baseline is defined as a negative RT-PCR test for SARS-CoV-2 and a negative serology test based on bAb specific to SARS-CoV-2 nucleocapsid on or before Day 1.

Study day relative to the first injection will be calculated as below:

- a) study day prior to the first injection will be calculated as: date of assessment/event
 date of the first injection;
- b) study day on or after the date of the first injection will be calculated as: date of assessment/event date of the first injection + 1

Study day relative to the most recent injection will be calculated as below:

- a) study day prior to the first injection will be calculated as: date of assessment/event
 date of the first injection;

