6.3.2. Solicited Adverse Reactions

An AR is any AE for which there is a reasonable possibility that the test product caused the AE. The term "Solicited Adverse Reactions" refers to selected signs and symptoms occurring after injection administration during a specified post-injection follow-up period (day of injection and 6 subsequent days). The solicited ARs are recorded by the subject in eDiary. The occurrence and intensity of selected signs and symptoms is actively solicited from the participant during a specified post-injection follow-up period (day of injection and 6 subsequent days), using a pre-defined checklist (i.e., solicited ARs).

The following local ARs will be solicited by the eDiary: pain/tenderness at injection site, erythema (redness) at injection site, swelling/induration (hardness) at injection site, and groin or underarm swelling or tenderness ipsilateral to the side of injection.

The following systemic ARs will be solicited by the eDiary: fever, irritability/crying, sleepiness, and loss of appetite.

The AR categories are presented in Table 7 in the protocol.

The solicited ARs will be graded based on the grading scales presented in Table 7 in the protocol, modified from the Toxicity Grading Scale for Healthy Adult and Adolescent Volunteers Enrolled in Preventative Vaccine Clinical Trials (DHHS 2007). Investigator will assess Grade 4 events (with exception of fever).

If a solicited local or systemic AR continues beyond 7 days post injection, the participant's parent(s)/ LAR(s) should notify the site to provide an end date to close out the event on the reactogenicity page of the eCRF.

All solicited ARs (local and systemic) will be considered causally related to injection.

Analyses of solicited ARs will be provided by study part and treatment group for each injection (first or second) based on the associated subset of Solicited Safety Set, i.e. First (Second) Injection Solicited Safety Set, unless otherwise specified.

The number and percentage of subjects who reported each individual solicited local AR (has a toxicity grade of Grade 1 or greater) and solicited systemic AR (has a toxicity grade of Grade 1 or greater) during the 7-day follow-up period after each injection will be tabulated by vaccination group, toxicity grade, and injection (i.e., first or second injection). The number and percentage of subjects who reported each individual solicited AR will also

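### The supervised eDiary entry about 30 minutes after injection is enough for entry to the Solicited Safety Set, so solicited reaction rates can be biased low by an unknown amount

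*SAP*

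**What the plan says.** **Entry to the set.** SAP 5.10 takes infants in the Safety Set "who contribute any solicited AR data, i.e., have at least one postbaseline solicited safety assessment". For the first-injection set they must "have contributed any solicited AR data from the time of first study injection through the following 6 days"; the second-injection set mirrors this. No minimum number of diary days is set.

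**First diary entry.** In Protocol 8.10.2 parents "will record data into the eDiary starting approximately 30 minutes after injection under the supervision of the study site staff". Home entries follow on the day of injection and the next 6 days.

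**Tables.** SAP 6.3.2 analyses solicited reactions "for each injection (first or second) based on the associated subset of Solicited Safety Set". The numerator is infants reporting a reaction that "has a toxicity grade of Grade 1 or greater". Tables by day of reporting are also planned.

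**Denominator.** SAP 6.1: "The denominator for all percentages will be the number of subjects in that vaccination group within the analysis set of interest, unless otherwise specified". SAP 6.3.2 names no other denominator. SAP 6.1 imputes nothing for missing diary days.

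**Other capture routes.** Protocol 8.10.2 has staff review the diary with parents 7 days after each injection (Day 8 and Day 64), and in Part 1 also at Day 4 and Day 60. Protocol 8.11.3 sends a reaction that the parent reported but did not enter in the diary to the Reactogenicity page of the eCRF. However, Protocol 8.10.2 makes the eDiary the sole permitted source for solicited reactions. SAP 6.3.2 mentions combining the two sources, by maximum grade, only in its sentence about listings.

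**The concern.** The set is meant to confine the reactogenicity tables to infants with reactogenicity data. The supervised entry satisfies the rule for practically every injected infant, so the set does little filtering. An infant whose parent enters nothing after leaving the site stays in the denominator and can reach the numerator only through the eCRF.

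The 30-minute entry says little about fever. Infants febrile before injection are rescheduled, and in Study mRNA-1273-P204 "Fever was most commonly reported on Day 1 or Day 2 after any vaccination". Protocol 8.10.2 also allows temperatures and redness or swelling measurements reported a day late to be left out of the analysis. A late fever report can then leave the numerator while the infant stays in the denominator.

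Solicited reactions are the first-listed primary safety endpoint in both parts (SAP 3.1), and Part 1 results inform the Part 2 dose level. The planned outputs would not show the problem. No diary-completion table or missing-diary sensitivity analysis is planned, and the disposition table in SAP 6.2.1, which gives the Solicited Safety Set as a percentage of the Safety Set, could read near 100% even if many home diaries were empty.

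**Working it through.** **The plan's own figure.** The only safety-precision figure is in Protocol 9.3 and SAP 4.3: at least a 90% chance of seeing one or more infants with an AE at a true rate of 1%, with about 300 infants. Check: 1 - 0.99^300 = 95.1%. It holds and this point does not affect it. The documents state no expected reaction rate or diary-completion rate for this trial, so the values of p, m and r below are assumptions.

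**Formula.** Let N be the infants in the set. Assume that those with only the 30-minute entry had no reaction recorded at that entry, and that their true rate is also p.

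- Reported numerator: N x p x (1 - m) + N x p x m x r
- Reported rate: p x [1 - m x (1 - r)]
- Bias: -p x m x (1 - r)

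**Bias in percentage points at r = 0:**

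| True rate p | m = 5% | m = 10% | m = 20% |
|---|---|---|---|
| 10% | -0.5 | -1.0 | -2.0 |
| 25% | -1.25 | -2.5 | -5.0 |
| 50% | -2.5 | -5.0 | -10.0 |

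At r = 0.5 every entry halves; at r = 1 every entry is zero.

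**Example with intervals.** N = 300, 30 infants with only the 30-minute entry, 68 infants with a reaction, r = 0.

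- Whole set: 68/300 = 22.7% (95% Clopper-Pearson 18.1 to 27.8)
- Infants with later data: 68/270 = 25.2% (20.1 to 30.8)

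**Part 2 contrast.** Assume true rates of 25% and 10%, m = 10% in both arms and r = 0. The reported rates are 25% x 0.9 = 22.5% and 10% x 0.9 = 9.0%. The difference falls from 15.0 to 13.5 points; the ratio stays at 2.5.

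**By-day tables.** If a share d of the set has no entry on a given day and nothing is recovered, that day's rate is multiplied by (1 - d). On Days 2 to 7, d is at least m, because partly completed diaries add to it. Dilution is therefore at least as large as in the 7-day rate.

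**Small arm.** SAP 7 reports that Part 1 Arm 2 paused at 18 infants. One infant with an empty home diary is 1/18 = 5.6% of that denominator.

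**Entry through the Reactogenicity page.** That page is completed when a reaction occurred, so using it as an entry route selects reactors. Take N = 300, p = 25%, m = 10%: 75 true reactors, of whom 7.5 are among the 30 infants without later diary data.

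- r = 1: whole set 75/300 = 25.0%, which is correct. With page-based entry, 75/(270 + 7.5) = 75/277.5 = 27.0%.
- r = 0.5: whole set (67.5 + 3.75)/300 = 23.75%. With page-based entry, 71.25/273.75 = 26.0%.

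Page-based entry replaces a possible downward bias with an upward one.

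**The case against.** The case against has five parts.

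- **Denominator.** SAP 6.1 lets a table specify another denominator and allows a row for missing data where the shells call for it. The shells are not in the documents, so a different denominator cannot be excluded. This stands as a caveat, but the SAP text itself sets only the default.
- **Recovery.** Diary reviews take place at Day 8 and Day 64. Part 1 adds clinic visits at Day 4 and Day 60, with temperature measured, soon after the fever window. Every contact includes a question about changes in health, and parents must agree at consent to complete the eDiary. All of this lowers m or raises r, and it stands. It is weakened by the conflict between Protocol 8.10.2 and 8.11.3, and by the SAP's silence on whether eCRF-only reactions enter the rate tables.
- **Consequences.** The analyses are descriptive, with no hypothesis attached. The pause rules in Protocol 7.4 count dosed or enrolled participants, not this set. With equal m and r, the vaccine-to-placebo ratio is unaffected. This stands and limits the weight of the point.
- **Origin of the rule.** Admission on any solicited data is in Protocol Table 8. Redefining the primary set in the SAP alone would depart from it.
- **Stronger readings.** A reader might infer that the rates are biased low, that every infant without a home diary is analysed as free of reactions, or that Part 1 dose selection is compromised. The documents support none of these. They give neither m nor r, they provide recovery routes, and follow-up is densest in Part 1.

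**Conclusion.** The point holds as a conditional one. As written, the entry rule and default denominator allow solicited reaction rates, and more so by-day rates, to be biased low by p x m x (1 - r). At an assumed true rate of 25% with no recovery, that is 1.25 points at m = 5% and 2.5 points at m = 10%. It vanishes if every infant has later diary data or every missed reaction reaches the tables through the eCRF.

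This rests on three things: the shells do not set a different denominator; infants with only the 30-minute entry had no reaction recorded then; and their reaction rate resembles that of the others. If that rate differs, p in the bias formula is the rate among those infants. The actual size cannot be determined from the plan, and the planned outputs would not show it. A change is worth making because the endpoint is primary for safety and the remedy uses data already collected.

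**What to change.** 1. In SAP 6.3.2, use infants with an eDiary entry on that day as the denominator for by-day percentages. For Day 1, state whether the supervised entry alone counts; if it does, the change has no effect on that day.
2. Add an analysis of each solicited reaction rate, at least as a sensitivity analysis, limited to infants with one or more eDiary entries after the supervised site assessment, or a documented Day 8 or Day 64 diary review whether its finding was positive or negative. Do not admit infants on a Reactogenicity-page entry alone.
3. Tabulate diary completion by day, arm and injection.
4. State whether reactions found only on the eCRF enter the rate tables, and reconcile Protocol 8.10.2 with 8.11.3 on permitted sources.

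The cost is a few SAP sentences, some denominator programming, slightly smaller denominators and slightly wider Clopper-Pearson intervals (in the example above, 10.7 points wide instead of 9.7). No new data are needed. If the primary set itself is redefined instead of adding a sensitivity analysis, Protocol Table 8 must be aligned.
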